#### **Process measures**

Patient participant and ICT staff perceptions/experience will be assessed via telephonic qualitative interviews with a sample of patient participants and SMH clinical staff to examine perceived barriers and facilitators to efficient and effective implementation of TEAM and TECH and to identify strategies for improvement and scalability of SMH to other chronic diseases.

Integrity of care/fidelity: For both interventions, we will track usage information such as time spent on each session in each arm, techniques covered in practice, techniques practiced, and total number of sessions and techniques completed. For the TEAM arm, the social workers will track if other types of therapy modalities were included from a comprehensive list that can be quantified. For the TECH arm, text messaging from the behavioral coaches will be reviewed for fidelity as part of routine care. Prescription of adjunctive psychotropic medications as part of stepped behavioral care will be tracked in both arms.

## **Study Population**

Our study population will comprise IBD patients receiving care at one of the three included SMHs with a confirmed diagnosis of Crohn's or UC, age 18 to 60 with BH symptom severity in the mild to severe range, defined as a score of >=6 on either depressive or anxiety severity scales (PHQ-4).

## **Inclusion/Exclusion Criteria**

#### **Inclusion Criteria**

Individuals who (1) are age 18-60; (2) have a diagnosis of Crohn's or UC; (3) have mild-to-severe behavioral health symptoms, defined as >=6 on either depressive or anxiety severity scales (PHQ-4); (4) consent to be randomized; (5) must have a smartphone; and (6) speak English.

#### **Exclusion Criteria**

Individuals who are (1) not able to speak English; (2) do not have a smartphone; and/or (3) exhibiting acute BH symptoms that require a higher level of treatment (e.g., suicidality, active eating disorder).

## **Study Duration/Study Timeline**

February 1, 2019 – June 30, 2019: Pre-Implementation Period July 1, 2019 – March 28, 2025: Implementation Period March 29, 2025 – September 30, 2026: Post-Implementation Period

## **Statistical Analysis Plan**

## **Sample Size and Power Calculations**

The bundles of TEAM and TECH services have been tested as packages. For the TEAM approach, we evaluated the feasibility, durability, and impact of the IBD specialty medical home for 346 IBD patients after one year of enrollment. In the year following enrollment, there was a significant reduction in IBD disease activity for both UC (p=.0003) and CD (p=.002), unplanned care (both ER visits (p<.0001) and hospitalizations (p=.008), while there was an observed improvement in health-related quality of life (p<.0001), depression (p<.0001) and anxiety (p=.02). For the TECH approach, a combination of digital tools- an app based cognitive behavioral program, remote monitoring and telepsychiatry (TECH) was compared to behavioral treatment as usual (control) using a randomized trial prospective design for patients with IBD with anxiety and/or depression. There was a significantly greater reduction in anxiety in the TECH group over 3 months (delta 5.6); CI (3.9, 7.6); p<.0001; n=34) than in the control group (delta 2.5; CI (0.5, 4.6); p=.02; n=35. There was also a greater reduction in depression (delta 2.6 CI (0.6, 4.6); p=.01 in the active versus control group (delta=.0.4; CI (-2.2, 3.1); NS). 76 Ninety-six percent of patients in TECH group engaged with the digital CBT program and participated in remote monitoring with 69% completing a clinically meaningful number of sessions. Both studies were conducted in "real world" clinical setting and powerfully show how both approaches can provide powerful solutions in improving health care delivery in sustainable ways.

Aim 1: We calculated statistical power for the target sample size of 675, with approximately 337 participants enrolled into both TEAM and TECH. After adjusting for the multiple testing in Aim 1 (2 tests) and considering 25% attrition, a sample size of 505 (approximately 252 per treatment group) will provide over 99.9% power for the hypothesis test for Aim 1. Among patients enrolled in the specialty medical home at that time who met active behavioral criteria (PHQ-4 >= 6), there was a significantly greater change in TECH (n=73; ES .49) versus TEAM (n=106; ES .36) for the behavioral composite but both approaches were associated with significant change over time (p=.005). Both approaches were also associated with significant improvement in the biological composite for both TEAM (ES .22) and TECH (ES .16). With the IBD SMH models of care being clinically operational at all three sites, we are collecting ongoing useful and robust information that has been published. In our most recent analyses of our clinical research registry tracking our TEAM approach (n=280), our most recent analyses show effect sizes comparable to these initial findings for both approaches.

Aim 2: We considered both subgroup analyses and formal tests of moderation. Subgroup analyses – Based on current data, our subgroups are relatively evenly proportioned. We expect that the smallest subgroup will be 42% of the sample and the largest will be 58% of the sample. Thus, our expected subgroup sizes after 25% attrition are between 212 and 293 for projected enrollment. For this range of subgroup Ns, we expect 0.80 power to detect small treatment effects ranging between 0.26 and 0.30. Moderation – We used Monte Carlo methods (100 runs) to simulate the binary moderator (M) and treatment (X) (both p=0.5), assuming M independent of X as expected in a randomized trial. Considering a range of effect sizes for B1, B2, and B3, we estimated the outcome Y as Y=B1\*X+B2\*M+B3\*X\*M+ $\varepsilon$ , where  $\varepsilon$ ^N(0,1). We averaged across

scenarios to determine the typical effect of B3 that can be detected with our current and projected sample sizes after 25% attrition. B3 can be interpreted as the difference between the treatment effect size among those with M=0 (D0=B1). With our projected sample sizes (N=505 after 25% attrition), we expect 0.80 power to detect a significant interaction when the magnitude of B3 is at least 0.50. To provide context for these effect sizes, we note that a B3 of 0.50 could correspond, for example, to a moderate effect of X in one subgroup (e.g., D1=0.60) and a small effect of X in the other subgroup (e.g., D0=0.10).

Our sample size calculations are consistent with the literature for both TEAM and TECH for behavioral and physical disease severity outcomes and there is literature supporting engagement and better outcomes with TECH approach with the younger cohort and those with higher eHealth-literacy. However, the research proposed will be beneficial even if we do not prove our hypotheses. For example, even if TEAM and TECH do not differ in Aim 1, the results can still suggest that TECH is feasible and allows TEAM to be utilized more efficiently. In Aim 2, even if we do not show a strong differential impact of the interventions based on IBD activity, we will still learn valuable information about which subgroups of behaviorally complex IBD patients have highest engagement and impact with each approach.

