## **Aims**

This study aimed to compare the effectiveness of two evidence-based, patient-centered behavioral approaches implemented within three existing medical homes: **TEAM**, a high-human touch multidisciplinary team-based approach delivered at point-of-care, and **TECH**, a low-human touch technology-based approach delivered at the patient's convenience with the guidance of health coaches. The study focused on patient-centered outcomes, impact on healthcare utilization, determining which intervention worked best for whom, and potential scalability of the model to other healthcare environments and for other chronic conditions.

**Primary Aim 1:** Examine the impact of TEAM vs. TECH on two main patient-centered outcomes of IBD and BH symptom severity and secondary outcomes of functional impairment, healthcare utilization, quality of life, and self-efficacy.

**Hypothesis 1:** Both TEAM and TECH approaches will result in clinically meaningful improvement across all outcomes.

**Primary Aim 2:** Examine the impact of patient characteristics on clinical response to TEAM or TECH approaches and establish subgroups of patients who will benefit most from each approach. The study focused on baseline IBD activity and age as primary moderators but secondarily explored site, IBD diagnosis, and health literacy.

**Hypothesis 2a:** The TEAM approach will show greater effects in those with active IBD, while TECH will show greater effects in those with inactive IBD.

**Hypothesis 2b:** The TECH approach will improve outcomes more in younger patients.

**Primary Aim 3:** Examine IBD patient and provider perspectives on facilitators and barriers to efficient and effective implementation of TEAM and TECH and the potential for scaling the interventions and SMH model to other common chronic diseases and community care settings to inform high-quality, efficient ongoing implementation and dissemination

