Aim 1 will examine the impact of TEAM vs. TECH on the primary and secondary outcomes and will determine if changes in outcomes over time are different between the two groups. We will fit the GLMMs to associate each outcome with the intervention (TEAM vs. TECH) and other covariates of interest. To account for the within-patient correlation in longitudinal data and to reflect potential differences among three sites, we will add normally distributed random effects for patients and sites in addition to the fixed effects for intervention and covariates of interest. An inference of the intervention effects for each outcome will be carried out using Wald test based on the either F-distribution or Chi-square distribution as appropriate. For each outcome, the null hypothesis of homogeneous change in outcomes overtime between TEAM and TECH will be examined by testing the treatment-by-time interaction effect on each outcome. In the absence of significant interaction effects, the marginal difference in outcomes between TEAM and TECH will be examined using the same GLMMs without the interaction effect. All hypothesis tests for Aim 1 will be conducted at the overall significance level of 0.05. The score changes from baseline to each time point and their difference between TEAM and TECH will be estimated with 95% confidence intervals.

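### The over-99.9% power quoted for Aim 1 is tied to no contrast or effect size, and no effect size printed beside it supports that figure for the planned TEAM-versus-TECH test

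*Combined protocol and SAP*

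**What the plan says.** For Aim 1, Sample Size and Power Calculations starts from 675 enrolled, allows 25% attrition, and concludes that "a sample size of 505 (approximately 252 per treatment group) will provide over 99.9% power for the hypothesis test for Aim 1". The only statement about alpha in that paragraph is "After adjusting for the multiple testing in Aim 1 (2 tests". The adjustment method is not named, nor is it said whether the two tests are two outcomes or something else.

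The paragraph then gives effect sizes from earlier specialty-medical-home patients: "significantly greater change in TECH (n=73; ES .49) versus TEAM (n=106; ES .36) for the behavioral composite", and "significant improvement in the biological composite for both TEAM (ES .22) and TECH (ES .16". It does not say that any of these fed the power calculation, which SD standardizes them, or at what time point they were measured.

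Quantitative Analysis defines the Aim 1 test as a comparison of arms: "the null hypothesis of homogeneous change in outcomes overtime between TEAM and TECH will be examined by testing the treatment-by-time interaction effect". It continues: "In the absence of significant interaction effects, the marginal difference in outcomes between TEAM and TECH will be examined". Hypothesis 1, under Aims, is of another kind: "Both TEAM and TECH approaches will result in clinically meaningful improvement across all outcomes". That is improvement within each arm, not a difference between them.

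**The concern.** Power has meaning only for a stated contrast and effect. The Aim 2 text gives detectable effects (0.26 to 0.30 in subgroups, 0.50 for the interaction). The main comparison gives only a percentage.

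What is at stake is how a null result is read. The same section anticipates one: "even if TEAM and TECH do not differ in Aim 1, the results can still suggest that TECH is feasible". Beside a claim of near-certain power, a non-significant TEAM-TECH test could be taken as strong evidence that the arms are equivalent. The sample does not give that assurance for moderate differences. With unit SD and 252 per arm, the standard error of a simple difference is √(2/252) = 0.0891, so a 95% interval extends 1.96 × 0.0891 = 0.175 SD either side. An observed difference just short of significance at 0.025 is 2.241 × 0.0891 = 0.200 SD, and its upper 95% limit is 0.375 SD.

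**Working it through.** **Inputs.** From Sample Size and Power Calculations: 505 analysed, about 252 per arm (675 × 0.75 = 506); two tests; effect sizes .49 and .36 (behavioral, TECH and TEAM), .22 and .16 (biological, TEAM and TECH). From Quantitative Analysis: overall level 0.05. Assumed: Bonferroni, so 0.025 per test, two-sided (z = 2.241); equal arms; unit SD; no repeated-measures gain.

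**1. Can the stated figure be reproduced?** Yes, for change within one arm. Power = Φ(ES × √n − 2.241), with n = 252 and √n = 15.875.
- Behavioral, TEAM .36: 5.715 − 2.241 = 3.473, giving 99.97%.
- Behavioral, TECH .49: 7.779 − 2.241 = 5.537, giving more than 99.99%.
- Biological, TEAM .22: 3.492 − 2.241 = 1.251, giving 89.5% (89.1% with the noncentral t).
- Biological, TECH .16: 2.540 − 2.241 = 0.299, giving 61.7% (61.2% with the noncentral t).

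Pooling all 505 as one group, the biological figures are 99.7% (.22) and 91.2% (.16), still short of 99.9%. The within-arm reading therefore works for one primary outcome and not for the other.

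**2. What does the planned between-arm test need?** Detectable difference = (z for alpha + z for power) × √(2/252).
- At 0.025, 80% power: (2.241 + 0.842) × 0.0891 = 0.275.
- At 0.025, 99.9% power: (2.241 + 3.090) × 0.0891 = 0.475 (0.476 with the noncentral t).
- At 0.05, noncentral t: 0.250 for 80% and 0.451 for 99.9%.

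**3. What do the printed effect sizes imply, if read on a unit-SD scale?** Power = Φ(d/0.0891 − 2.241), plus a small opposite tail.
- Behavioral, .49 − .36 = 0.13: 1.459 − 2.241 = −0.782, giving about 22%.
- Biological, .22 − .16 = 0.06: 0.674 − 2.241 = −1.568, giving about 6%.

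**4. Is that scale right?** It cannot be confirmed. With a common unit SD, 0.13 between groups of 73 and 106 has standard error √(1/73 + 1/106) = 0.152, so z = 0.855 and p = 0.39. The plan calls the same difference significant. Either the effect sizes are on another scale or the significance statement refers to something else.

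**5. Consistency with Aim 2.** The plan gives 80% power for effects of 0.26 to 0.30 at subgroup sizes 293 to 212. A plain two-sample calculation at two-sided 0.05, (1.960 + 0.842) × √(4/N), gives 0.327 and 0.385. The plan's figures would need a variance factor of about (0.26/0.327)² = 0.63 and (0.30/0.385)² = 0.61, which is not explained. A restated Aim 1 figure has to be on the same basis. Otherwise the full sample would seem to detect no smaller an effect than a subgroup does.

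**The case against.** The strongest defence is that the figure is a correct answer to Hypothesis 1, which is about improvement in each arm; the two tests might even be the two arms. Step 1 shows that this works for the behavioral composite, so the number has a plausible origin. Two things remain. The text attaches it to the Aim 1 hypothesis test, which the analysis section makes a comparison of arms. And Hypothesis 1 covers all outcomes, yet the biological effect sizes do not reach 99.9%.

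A second defence is that larger differences can be found. Using TECH's .49 as a between-arm effect gives 5.500 − 2.241 = 3.259, or 99.94%, but .49 is TECH's own change. The earlier digital-tools trial described in the same section also shows a large anxiety difference, but its comparator was behavioral treatment as usual, not TEAM.

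A third is that repeated measures add precision. They may, but the amount depends on a correlation, a visit schedule and a model that the power paragraph does not give. The marginal model in particular is described without baseline adjustment, so no favourable figure can be assumed for it.

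It is also fair that enrollment is complete, that 95% confidence intervals for the TEAM-TECH difference in change are already planned, and that the plan nowhere claims equivalence. A null result is said only to suggest that TECH is feasible. The risk of misreading is therefore a risk, not something the plan commits to.

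**Conclusion.** The statement of over 99.9% power is not supported for the test that the plan describes. On a single comparison with 252 per arm, unit SD and two-sided 0.025, that power needs about 0.476 SD between arms; 80% needs 0.275 SD. No effect size printed in the Aim 1 power paragraph, used for the contrast it describes, yields 99.9% for the between-arm test, or for both primary outcomes under Hypothesis 1.

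Three stronger readings are tempting and should be resisted.
- That actual power is 22% or 6%. Those values hold only on a unit-SD scale that the pilot's own significance statement contradicts, and the within-patient correlation is not given. True between-arm power cannot be determined from the documents.
- That the plan reports no TEAM-TECH difference at all. It does claim greater behavioral change in TECH, but not on a defined scale and not as the power input.
- That 99.9% is simply a miscalculation. It matches within-arm behavioral change; the fault is that it is attached to a different test.

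This should be corrected. The consequence is for interpretation, not for the conduct or size of the trial.

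**What to change.** Recover the original power inputs, then revise the Aim 1 power paragraph:
- Replace the 99.9% sentence with a detectable difference, for example: *With 252 per arm after 25% attrition and two-sided 0.025, a single TEAM-versus-TECH comparison has 80% power for a standardized difference of about 0.275 (unit SD, no repeated-measures gain).* State what the two tests are. Give any repeated-measures figure only with its correlation, visits and model, and say whether it is for the interaction or the marginal test.
- If 99.9% is kept, label it as power for within-arm behavioral change only, and print the biological figures (about 89% and 61%) beside it.
- Put Aim 1 and the Aim 2 subgroup figures on the same variance basis, and state that basis.
- Define the SD and time point behind the pilot effect sizes, so that .49 against .36 can be reconciled with the claim of a significantly greater change.
- State that a non-significant Aim 1 test will be interpreted through the planned 95% confidence intervals, not as evidence of no difference.

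The cost is the rewording of one paragraph, an alignment with the next, and a less favourable headline figure. No new patients, data or tests are needed.

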Given our study Aim 2 to understand how TEAM and TECH provide different benefits to individuals with different characteristics, we will explore potential heterogeneity of treatment effects in clinical response between subgroups of patients defined using patients' baseline characteristics. All co-variates will be identified a-priori. For Aim 2.a, we will examine whether and how the effect of TEAM and TECH approaches on BH symptom severity varies between patients with a high level of IBD disease activity (HBI or UCAI score > 4) and patients with low disease activity (HBI or UCAI score <=4) at baseline. IBD disease activity and effect of TEAM and TECH approach will also be assessed using a recently developed, validated, and preferred measure of disease activity for Crohn's disease and UC (PRO-2). 63,64 For statistical inference, we will fit the same GLMMs as described in Aim 1 and will include the higher order interaction terms with subgroups of patients defined by IBD activity. The null hypothesis of homogenous treatment effect between patients with high and low IBD activity in each outcome will be examined via interaction analysis (three-way interaction of time, treatment, and subgroup of IBD severity; two-way interaction of treatment and subgroup of IBD severity in the absence of a significant three-way interaction effect) using Wald test based on either F-distribution or Chisquare distribution as appropriate at the significance level of 0.05. In the presence of statistically significant treatment heterogeneity, the score change in BH symptom severity from baseline to each time point and their difference between TEAM and TECH will be estimated with 95% confidence intervals for subgroup of patients defined by IBD severity. For Aim 2.b, we will explore whether and how the effect of TEAM and TECH approaches on primary outcomes varies between young (age<=30) and older (age>30) patients. We will also examine the impact of TEAM and TECH on patients with differing IBD diagnoses, namely ulcerative colitis and Crohn's disease. Further, we will explore the effect of site differences, behavioral health history, insurance type (public vs. not), e-health literacy, and medications on response to TEAM or TECH intervention as secondary and exploratory analyses. For statistical inference, the same hypothesis test and statistical model described in Aim 2.a will be used. We will make a Bonferroni correction for multiple testing in order to conduct subgroup analyses at the overall significance level of 0.05. In the presence of statistically significant treatment heterogeneity,

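### Aim 2 power: the subgroup effects of 0.26-0.30 and the interaction of 0.50, both given 80% power, do not fit one effect-size scale, alpha and model

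*Combined protocol and SAP*

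**What the plan says.** All references are to the Statistical Analysis Plan in the combined protocol and SAP.

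**Sample Size and Power Calculations, Aim 2, subgroup analyses.** The subgroups are expected to be 42% and 58% of the sample: "our expected subgroup sizes after 25% attrition are between 212 and 293 for projected enrollment". The claim follows: "For this range of subgroup Ns, we expect 0.80 power to detect small treatment effects ranging between 0.26 and 0.30". No test, alpha, sidedness, SD or correlation is given for it.

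**Same section, Aim 2, moderation.** A simulation with 100 runs uses a binary treatment X and a binary moderator M, each with probability 0.5, and standard normal errors. For N=505 the result is: "we expect 0.80 power to detect a significant interaction when the magnitude of B3 is at least 0.50". The plan illustrates this as an effect of 0.60 in one subgroup and 0.10 in the other, so it reads B3 as a difference between subgroup effects.

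**Quantitative Analysis.** The analysis model for Aim 1, reused for Aim 2, is a longitudinal mixed model: "we will add normally distributed random effects for patients and sites in addition to the fixed effects". The Aim 2.a interaction is tested "using Wald test based on either F-distribution or Chisquare distribution as appropriate at the significance level of 0.05". Later in the Aim 2 text: "We will make a Bonferroni correction for multiple testing in order to conduct subgroup analyses at the overall significance level of 0.05". The number of tests is not given. The Aim 1 power statement does mention multiplicity ("After adjusting for the multiple testing in Aim 1 (2 tests) and considering 25% attrition"); the Aim 2 power statements do not.

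**The concern.** The two power statements are adjacent, concern the same patients and are both expressed as standardised effects. Since 212 + 293 = 505, the two subgroups together are the sample used for the interaction. A reader will therefore put the figures on one scale, as the plan's own 0.60 versus 0.10 example invites. Once that is done, they disagree.

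Aim 2 is one of the plan's primary aims, and the power section says that something will be learned even without a strong differential impact by IBD activity. Reading such a null result requires knowing what difference the trial could have detected. As written, that could be 0.26-0.30 or 0.33-0.39 within subgroups, and 0.40 or 0.50 for the interaction.

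**Working it through.** **Inputs.** From the power section: N=505 after attrition; subgroups of 212 and 293; power 0.80; X and M each with probability 0.5; residual SD 1 (stated for the moderation simulation only). From Quantitative Analysis: alpha 0.05 for the Aim 2.a interaction. Two-sided testing is stated there for the baseline comparisons and is assumed here. The multiplier for 80% power is 1.960 + 0.842 = 2.802.

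**Step 1: reproduce the interaction figure.** With four equal cells, SE(B3) = sqrt(16/505) = 0.178.
- Detectable B3 = 2.802 × 0.178 = 0.499.
- Power at 0.50 = Φ(0.50/0.178 − 1.960) = 80.2%.
- With a 42/58 moderator split instead, detectable B3 is 0.505 and power at 0.50 is 79.2%.

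The printed 0.50 therefore reproduces at two-sided 0.05 with residual SD 1.

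**Step 2: subgroup figures on that basis.** With 1:1 arms, SE = sqrt(4/N).

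| Subgroup N | SE | Stated effect | Power, normal (noncentral t) | Detectable at 80%, normal (noncentral t) |
|---|---|---|---|---|
| 212 | 0.137 | 0.30 | 58.9% (58.5%) | 0.385 (0.387) |
| 293 | 0.117 | 0.26 | 60.5% (60.2%) | 0.327 (0.328) |

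Rounding does not close the gap: effects of 0.305 and 0.265 give 60.3% and 62.1%. One-sided 0.05 gives detectable effects of 0.34 and 0.29. Pre-attrition sizes (283.5 and 391.5) at two-sided 0.05 give 0.33 and 0.28.

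**Step 3: the reverse check, which needs no choice of SD.** B3 is the difference between two independent subgroup effects, so its variance is the sum of theirs. At a common alpha, power, scale and model, detectable effects are proportional to standard errors. Hence

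implied detectable B3 = sqrt(0.26² + 0.30²) = sqrt(0.0676 + 0.0900) = 0.397.

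The printed value is larger by a factor of 0.50/0.397 = 1.26. On the Step 1 basis, power at 0.397 is about 61%. Monte Carlo error does not explain this: with 100 runs it is sqrt(0.8 × 0.2/100) = 0.04 per scenario.

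**Step 4: what would make 0.26-0.30 attainable.** Relative to Step 2, the SD must shrink by 0.30/0.385 = 0.78 (N=212) and 0.26/0.327 = 0.79 (N=293), which is a variance factor of about 0.61 and 0.63. Assume equal variances and a common correlation r between visits (compound symmetry); the plan gives no value of r.
- *Mean of two follow-ups, baseline-adjusted:* the factor is (1 + r)/2 − r². Its maximum is 0.5625, at r = 0.25. Detectable effects are then at most 0.290 and 0.246, so the range is reached at any r from 0 upwards.
- *Single visit, baseline-adjusted:* the factor is 1 − r². This needs r of about 0.63 and 0.61. At r = 0.62 the detectable B3 in outcome-SD units is 0.39.
- *Change from baseline to one visit:* the factor is 2(1 − r). This needs r of about 0.70 and 0.68. At r = 0.5 the factor is 1, and the detectable effects return to 0.385 and 0.327.

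**The case against.** The strongest reply is that the unit-variance equation belongs to the moderation simulation and nothing says that it underlies the subgroup figure. The planned analysis is the longitudinal mixed model, and the compensation schedule shows self-report surveys at baseline, 6 and 12 months. With two follow-ups, 0.26-0.30 can be an ordinary or even cautious figure. The two numbers might also differ only in scale: 0.50 in residual-SD units at r = 0.62 is 0.50 × sqrt(1 − 0.62²) = 0.39 in outcome-SD units, almost the implied 0.397. Finally, Aim 2 inference rests on the interaction test, with subgroup differences estimated only after significant heterogeneity, and the interaction figure reproduces.

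Much of this stands. A reader might infer from Step 2 that true subgroup power is 58-60% and that the stated 80% is false. The documents do not support that, because the longitudinal model is also part of the plan and some of its contrasts reach the range.

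The reply does not remove the inconsistency. Whether the range is reached depends on the contrast. The plan tests treatment-by-time first (with the subgroup added for Aim 2), and a baseline-to-one-visit change needs r of about 0.70. The plan links no contrast, correlation or scale to 0.26-0.30. If a longitudinal gain does lie behind that figure, the neighbouring B3 is either computed without it or expressed on another scale, and the reader is not told which.

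A reader might also want to put a number on the power lost to the Bonferroni correction. That would require a family size, which the plan does not give, so no such figure is offered.

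**Conclusion.** The point holds as an inconsistency between two stated power figures for a primary aim. On the basis that reproduces B3 = 0.50 (two-sided 0.05, residual SD 1, 1:1 arms), the subgroup effects have about 58-60% power and the detectable effects are about 0.33-0.39. Taking 0.26 and 0.30 as given, the detectable B3 is about 0.40. The first statement rests on applying the simulation's unit SD to the subgroups. The second needs only a common scale, alpha and model.

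It is not shown that 0.26-0.30 is unattainable, nor that the sample size is inadequate. Enrolment closed in February 2024, and neither the sample size nor the tests would change. What is affected is the sensitivity that the plan claims and how a null Aim 2 result should be read. The point should be fixed, at modest consequence.

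**What to change.** State one basis for both Aim 2 figures: the test or contrast (including which visits), alpha and sidedness, the effect-size scale (residual or outcome SD), and any correlation assumed. Then do one of the following:

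- keep B3 = 0.50 and restate the subgroup detectable effects as about 0.33-0.39 on the basis used for B3; or
- keep 0.26-0.30, name the longitudinal contrast and correlation that produce it, and restate B3 on that scale as about 0.40.

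In Quantitative Analysis, say which Aim 2 tests the Bonferroni correction covers and how many there are, and compute the restated figures at the corrected alpha for those tests.

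The cost is a few sentences in the power section and one in Quantitative Analysis. The stated sensitivity may look less favourable. No patients are added and no test changes.
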